6.4.1 Imaging Day-1, Rest/Stress [⁶⁸Ga]Galmydar PET MPI

6.4.1.1 Rest [⁶⁸Ga]Galmydar PET

- Perform all required safety assessments pre-injection of [⁶⁸Ga]Galmydar and monitor ECG rhythm and HR as described above. Obtain baseline VS and ECG (BP, HR, and RR) within 15-min [⁶⁸Ga]Galmydar pre-injection;
- Administer an intravenous bolus injection of 4 mCi ± 20% (3.2–4.8 mCi) with a mass of ≤ 10 µg of [⁶⁸Ga]Galmydar followed by a 10 mL normal saline flush.
- Begin up to a 30-min list-mode data acquisition for a single bed position at the level of the heart immediately post-injection;
- Remove subject from the scanner. Transfer participant to CTRU for a break.
- The interval between the rest and stress [⁶⁸Ga]Galmydar PET acquisitions *should be no less than 2 hours and no greater than 4 hours*.

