1.1 Significance

Existing state-of-the art MPI tracers have certain limitations, such as low sensitivity, poor spatial resolution, attenuation artifacts, slow liver clearance, and nonlinearity of MBF at high flow rates.

To overcome these shortcomings, new MPI agents are desired. Utility of PET MPI agents, such as ¹³N-ammonia, and H₂¹⁵O is limited due to the requirement for proximity to a multimillion dollar cyclotron. In addition, myocardial perfusion examinations using ⁸²RbCl₃ suffer from low first pass extraction, low spatial resolution because of the higher positron range, and short radionuclide half-life due to both potential oversaturation of the detectors at the beginning of the acquisition due to injected high dose, and low count statics and suboptimal signal/noise ratios at later time points. Conversely, Gallium-68 based agents offer tremendous advantages as potential PET MPI agents and are likely to widely resolve these shortcomings.

Using Gallium-68, Galmydar incorporates four important components into its pharmacophore design: a) a rationale built upon exploiting transporter-mediated efflux pathways (Pgp and BCRP substrates) to facilitate excretion from neighboring tissues, such as liver and blood, to allow high heart-to-liver and heart-to-blood ratios enabling high target/ background ratios, b) moderately hydrophobic cationic probes possessing a delocalized positive charge on their molecular surface to allow penetration of myocardium in response to favorable negative plasma- and mitochondrial transmembrane potentials, thereby producing high first-pass extraction and minimal washout from myocardium during imaging sessions, c) a PET agent that incorporates a generator-produced radionuclide, ⁶⁸Ga (t_{1/2} = 68 min), to allow production of the radiopharmaceutical independent of the availability of a nearby cyclotron, and d) a potential technology conducive for business models of kit distributions comprising a ligand with a long shelf-life, thereby enabling onsite production for imaging in clinics. These combined elements indicate that further development of [⁶⁸Ga]Galmydar and its translation is based upon the strong scientific premise.

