5 INVESTIGATIONAL STUDY DRUG

5.1 Drug Description

The investigational study drug is ⁶⁸Ga-Galmydar. Gallium-68 is a positron-emitting radioisotope that is produced from a ⁶⁸Ge/⁶⁸Ga generator with a physical half-life of 67.7 minutes. An Investigator's Brochure does not exist for this radioactive drug. The pharmacological properties and formulation are described in detail in the Chemistry, Manufacturing, and Control Data section of the IND application.

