8 IMAGE PROCESSING AND ANALYSIS

8.1 Rest Stress Group

8.1.1 PET Images

All images will be reconstructed at 5-min (a delay to allow for blood-pool clearance) using reconstruction matrix at 168 × 168 × 109, with a pixel size (2 × 2 × 2 mm). Scatter, decay, and random corrections will also be applied to the reconstructed images. Static myocardium perfusion and gated myocardial function images will be generated by skipping the first 5 minutes of the list mode data acquisition. Dynamic image sequence will be reconstructed for quantitative blood flow evaluation. Comparative quantitative blood flow will be evaluated with Carimas and also using QPET or 4DM software⁶⁵ available through our departmental image processing servers (MIM/Vista and Hermes). Myocardial image processing techniques will then be applied to the gated datasets. The myocardial wall segment analysis will be performed using the 17-segment American Heart Association model⁶⁶.

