11.3.2.2 Rest/Stress Group

Participants will receive two [⁶⁸Ga]Galmydar intravenous administrations, 4 mCi during rest and 6 mCi during stress for the PET MPI performed on Imaging Day-1. The effective dose for a single intravenous administration of 6 mCi of [⁶⁸Ga]Galmydar is 0.62 rem and 0.41 rem for a 4 mCi administration performed. The acceptable mass of [⁶⁸Ga]Galmydar is \leq 10 μ g per administration. On Imaging Day-2, participants will receive two single administrations each of 10 mCi of ¹³N-Ammonia during the rest and stress PET MPI.

- Rest/Stress [⁶⁸Ga]Galmydar PET MPI**

The effective dose for a rest and stress PET MPI study includes an intravenous administration of 4 mCi during the rest PET and an 6 mCi administration during the stress PET MPI, and two CT-AC scans with topogram is 1.40 rem.

- Rest/Stress ¹³N-Ammonia PET MPI**

The effective dose for a single intravenous administration of 10 mCi of ¹³N-Ammonia is 0.07 rem. The effective dose for a rest/stress ¹³N-Ammonia PET MPI study includes two administrations each of 10 mCi of ¹³N-Ammonia and two CT-AC scans is 0.51 rem.

- Total Rest/Stress PET MPI**

The total effective dose for Imaging Day-1, rest/stress [⁶⁸Ga]Galmydar PET MPI and Imaging Day-2, rest/stress ¹³N-Ammonia PET MPI study is 1.91 rem. This includes one administration each of ⁶⁸Ga-Galmydar, 4.0 mCi during rest and 6 mCi during stress, and two CT-AC scans and two administrations each of 10 mCi of ¹³N-Ammonia and two CT-AC scans.

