- j) PET/CT imaging: Obtain a low-dose CT-AC (50 mAs) prior to each rest and stress radiotracer injection. If the same IV line is used for both the regadenoson and radiotracer injections, wait 10-20 sec after the normal saline flush post regadenoson injection before injecting the radiotracer.

k) [⁶⁸Ga]Galmydar Imaging Day-1:

- *Rest PET*: Administer 4 mCi ±20% (3.2–4.8 mCi) of [⁶⁸Ga]Galmydar IV injection followed by a 10 mL saline flush and immediately begin up to a 30-min list-mode data acquisition for a single bed position at the level of the heart. The interval between the rest and stress [⁶⁸Ga]Galmydar PET acquisitions *should be no less than 2 hours and no greater than 4 hours*.
- *Stress PET MPI*: Administer a rapid (10-sec) regadenoson IV injection (0.4 mg/5 mL), followed by 5 mL saline flush; 30-sec post regadenoson injection, administer 8 mCi ±20% (6.4–9.6 mCi) of [⁶⁸Ga]Galmydar IV injection followed by a 10 mL saline flush. Begin up to a 30-min list-mode data acquisition for a single bed position at the level of the heart.

l) ¹³N-Ammonia Imaging Day-2:

- *Rest PET*: Administer an IV bolus injection of 10 mCi ±20% (8–12 mCi) of ¹³N-Ammonia followed by a 10 mL saline flush and immediately begin a 10-min list-mode data acquisition (if the anterior-posterior diameter of the chest is >50cm increase to 15-min) for a single bed position at the level of the heart. The interval between the rest and stress ¹³N-ammonia acquisitions should be *no less than 1-hour*.
- *Stress PET MPI*: Administer a rapid (10-sec) regadenoson IV injection (0.4 mg/5 mL), followed by 5 mL saline flush; 30-sec post regadenoson injection, administer 10 mCi ±20% (8–12 mCi) of ¹³N-Ammonia IV bolus injection followed by a 10 mL saline flush. Begin a 10-min list-mode data acquisition (if the anterior-posterior diameter of the chest is >50cm increase to 15-min) for a single bed position at the level of the heart.

m) Transfer [⁶⁸Ga]Galmydar participants to CTRU for post imaging safety assessments and discharge.

Discharge ¹³N-Ammonia participants from the CCIR.

n) Contact [⁶⁸Ga]Galmydar participants by phone within 2-3 days post [⁶⁸Ga]Galmydar injection.

[⁶⁸Ga]Galmydar and ¹³N-ammonia imaging visits will be separated by a minimum of 3-days and not before the follow-up phone call is complete for capturing participant adverse events following the administration of [⁶⁸Ga]Galmydar. If any of the days are not business days, the phone call may occur the following business day.

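### Same-day stress Galmydar scans carry leftover rest activity that the plan neither measures nor removes, so reversible defects look milder and stress uptake reads high by an amount the documents do not fix

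*Combined protocol and SAP*

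**What the plan says.** Rest and stress Galmydar injections are normally given on one day. Section 11.3.2.2 gives "4 mCi during rest and 6 mCi during stress for the PET MPI performed on Imaging Day-1". Sections 5.3 and 6.4.1 agree, with tolerances of 3.2–4.8 mCi at rest and 4.8–7.2 mCi at stress. Table 3, note k (Section 16), differs for stress: "administer 8 mCi ±20% (6.4–9.6 mCi) of [⁶⁸Ga]Galmydar IV injection".

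Section 6.4.1.1 sets the gap between the two acquisitions: it "should be no less than 2 hours and no greater than 4 hours". It does not say whether this runs start to start or from the end of the rest scan, which may last up to 30 minutes. Section 5.1 describes ⁶⁸Ga as a generator product "with a physical half-life of 67.7 minutes". Section 1.1 lists "minimal washout from myocardium during imaging sessions" among the design properties of the tracer. Section 6.4 lets some participants have rest and stress at separate visits.

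On processing, Section 8.1.1 says: "Scatter, decay, and random corrections will also be applied to the reconstructed images". Section 8.1.4 fits a one-compartment model with K1 and K2 and, beside them, only partial recovery and blood-pool spill-over. In Section 6.4.1.2 the stress list-mode starts once the tracer is in. Residual rest activity is not mentioned in any of these places.

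**The concern.** Two hours is 120/67.7 = 1.77 half-lives, so a visible part of the rest injection is still present when the stress tracer arrives. Decay correction rescales those counts but cannot tell which injection they came from.

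The leftover activity carries the rest pattern. In a territory that is normal at rest and underperfused at stress, it partly fills the stress defect and pulls SSS and SDS (Sections 8.1.2 and 9) towards normal. The readers are blinded to tracer and to stress agent, so they cannot allow for it. The same activity raises stress SUV and adds an offset to the stress time-activity curve. It therefore reaches stress K1, MFR, and the α and β extraction parameters that Section 8.1.4 derives by relating Galmydar K1 to ammonia MBF. Quantitative comparison with ammonia is part of the primary objective (Section 2.1).

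**Working it through.** **Inputs from the documents.** Half-life 67.7 min (Section 5.1). Rest activity 4 mCi, range 3.2–4.8 (Section 6.4.1.1). Stress activity 6 mCi, range 4.8–7.2 (Sections 5.3, 6.4.1.2, 11.3.2.2), or 8 mCi (Table 3). Interval 120–240 min. Rest scan up to 30 min. The plan states no residual figure, so there is none to reproduce.

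**Step 1: leftover activity.** Share r = (rest mCi ÷ stress mCi) × 2^(−t/67.7), physical decay only.

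| Case | Calculation | r |
|---|---|---|
| 4/6 mCi, 120 min | 4 × 0.2927 = 1.17; 1.17/6 | 19.5% |
| 4/6 mCi, 150 min (2 h after a 30-min rest scan) | 4 × 0.2153 = 0.861; 0.861/6 | 14.4% |
| 4/6 mCi, 240 min | 4 × 0.0857 = 0.343; 0.343/6 | 5.7% |
| 3.2/7.2 mCi, 120 min | 0.444 × 0.2927 | 13.0% |
| 4.8/4.8 mCi, 120 min | 1 × 0.2927 | 29.3% |
| 4/8 mCi (Table 3), 120 min | 1.17/8 | 14.6% |

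If rest and stress are 24 h apart, 1440/67.7 = 21.3 half-lives have passed and r is effectively zero.

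**Step 2: from injected activity to heart signal.** Retention in human myocardium at 2–4 h is not given. With half retained (assumption), the 2 h figure is 19.5%/2 = 9.8%. Let u be stress uptake per mCi in normal myocardium relative to rest (also not given). As a share of stress-deposited signal, the residual is r/u: 19.5% at u = 1 and 9.8% at u = 2.

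**Step 3: effect on a defect.** For a reversible defect with true defect-to-normal ratio d, the observed ratio is (u·d + r)/(u + r). With d = 0.50, r = 0.195 (2 h, full retention):

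- u = 1: 0.695/1.195 = 0.582, a 42% defect
- u = 2: 1.195/2.195 = 0.544, a 46% defect
- u = 3: 1.695/3.195 = 0.531, a 47% defect

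At 4 h (r = 0.057) and u = 1: 0.557/1.057 = 0.527, a 47% defect. For a matched scar the residual is scaled by d as well, so (u·d + d·r)/(u + r) = d and nothing changes.

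**Step 4: SUV ratio.** If stress SUV is normalised to the stress activity alone (assumption), the measured stress/rest SUV ratio is u + r. With full retention at 2 h, a true 2.0 becomes 2.0 + 0.195 ≈ 2.2.

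**Step 5: K1.** In noise-free one-compartment fits with fitted spill-over and an assumed blood curve, adding a constant retained residual raised stress K1 in every case tried. The size moved widely with the assumed blood curve, washout and retention. I therefore report the direction only.

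**The case against.** The strongest case against is that the leading figure overstates what is in the heart. A reader might infer that one fifth of the stress heart signal is old tracer. The documents do not support that: 19.5% is decayed injected activity, and it equals heart signal only with full retention and equal uptake per mCi. The low-washout property in Section 1.1 is a design statement about imaging sessions, which last up to 30 minutes per scan here, not a human measurement at 2–4 h. The kinetic model itself carries a washout constant. An end-to-start reading of the interval gives 14.4%. All of this stands and reduces the size.

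A reader might also infer a definite percentage inflation of K1. That does not stand: any such figure depends on assumed inputs, and combining full retention over 2 h with an appreciable K2 would be inconsistent.

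Nor do the documents show that the present/absent CAD read, or the kappa behind the sample size, would change. No link from defect contrast to reader category is given. The documents also give no half-life for ¹³N, so I put no number on the difference from ammonia.

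It can be said that fitting α and β against ammonia MBF absorbs a common shift in K1. It absorbs part of an average shift. But the residual affects stress and not rest, varies with interval and activity, and vanishes for participants split across days, so it is not a common shift. Section 8.1.4 also uses only left-ventricular means in its MFR analysis, which weakens any argument there about low-flow territories. Section 8.1.2 still reports regional flow.

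**Conclusion.** The point holds in a limited form. Followed as written, the plan biases same-day stress Galmydar data in a known direction: reversible defects look milder, and stress SUV, K1 and MFR read high.

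Leftover activity at nominal doses is 5.7–19.5% of a 6 mCi stress activity across the permitted interval, and 13–29% at 2 h across the dose tolerances. A true 50% reversible defect reads as about 42% in the least favourable nominal case (2 h, full retention, u = 1) and about 46–47% at u = 2–3. Less retention or a longer interval makes the effect smaller. Matched scar and separate-day participants are essentially unaffected. The size of the K1 and MFR bias is unknown, because human retention, stress uptake and the blood curve are not given.

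Unknown retention is a reason to measure the residual rather than to assume it away. For a scan acquired without a pre-injection frame, the residual can later only be modelled. Separately, the 6 mCi and 8 mCi stress figures conflict and must be reconciled.

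**What to change.** This point asks for no change to doses or interval.

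- **Acquisition.** After the CT-AC already planned before the stress injection, start list-mode at least one to two minutes before the tracer, which means before regadenoson. Leave the regadenoson-to-tracer timing as it is.
- **Processing.** Use the pre-injection frame, decay-corrected to each stress frame, to subtract residual activity from the static and gated stress images before scoring and before SUV is normalised. In the dynamic analysis, subtract it or fit it as a baseline term. State this in Sections 8.1.1 and 8.1.4.
- **Symmetry.** Apply the same step to the ammonia stress scan.
- **Checks.** Use the dosimetry group's 2 h and 4 h scans (Section 6.3) to estimate myocardial retention. Record the actual injection-to-injection interval and whether rest and stress were on separate days. State whether the 2–4 h runs start to start or end to start.
- **Consistency.** Reconcile Table 3, note k, with Sections 5.3, 6.4.1.2 and 11.3.2.2.

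The cost is a minute or two more of list-mode and one processing step, with no added injection or visit. A short low-count frame adds some noise to the subtracted data; smoothing it or lengthening it slightly limits that.

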6.4.1.2 Stress [⁶⁸Ga]Galmydar PET

- Perform all required safety assessments pre-injection of regadenoson and [⁶⁸Ga]Galmydar as described above. Monitor ECG rhythm and HR continuously during the PET scan;
- Administer a rapid (10-sec) regadenoson intravenous injection (0.4 mg/5 mL), followed by 5 mL saline flush;

- 30-sec post regadenoson injection, administer a maximum intravenous bolus injection of 6 mCi \pm 20% (4.8-7.2 mCi) with a mass of \leq 10 μ g of [⁶⁸Ga]Galmydar followed by a 10 mL normal saline flush. If the same IV line is used for both the regadenoson and radiotracer injection, wait 10 to 20 seconds after the normal saline flush post regadenoson injection before injecting the radiotracer;
- Begin up to a 30-min list-mode data acquisition for a single bed position at the level of the heart immediately post-injection;
- Perform all required safety assessments post-injection of ⁶⁸Ga-Galmydar, end of imaging and prior to discharge from the imaging facility as described above;
- Transfer participant to CTRU for post imaging assessments and procedures prior to discharge as described above.

6.4.2 Imaging Day-2, Rest/Stress ¹³N-Ammonia PET MPI

[⁶⁸Ga]Galmydar and ¹³N-ammonia imaging visits will be separated by a minimum of 3-days but not before the participant follow-up phone call is complete for capturing adverse events following the administration of ⁶⁸Ga-Galmydar. Participants will report to the CCIR. The PI, study cardiologist or trained designee will evaluate symptomatic patients to confirm there has been no change in clinical status since the [⁶⁸Ga]Galmydar PET MPI. If in the judgment of the investigator/designee the patient's clinical condition has changed since the [⁶⁸Ga]Galmydar imaging day, the patient may undergo the rest only ¹³N-ammonia PET imaging scan or be rescheduled for Imaging Day-2, ¹³N-ammonia PET MPI.

6.4.2.1 Rest ¹³N-Ammonia PET

- Review of concomitant medications and any changes in health between the rest/stress PET MPI imaging day-1, ⁶⁸Ga-Galmydar, and imaging day-2, ¹³N-ammonia;
- Confirm a negative urine pregnancy test for women of childbearing potential;
- Obtain baseline vital signs (BP and HR) pre and post ¹³N-ammonia injection as described above. Continue to monitor ECG-rhythm and HR until imaging is completed;
- Administer an intravenous bolus injection of 10 mCi \pm 20% (8–12 mCi) of ¹³N-ammonia followed by a 10 mL normal saline flush.
- Begin a 10-min list-mode data acquisition (if the anterior-posterior diameter of the chest is >50 cm increase to 15-min) for a single bed position at the level of the heart immediately post-injection;
- Obtain vital signs (BP and HR) and 12-lead ECG as required per clinical protocol;
- Remove patient from scanner for a break. The interval between the rest and stress ¹³N-ammonia acquisitions should be per the clinical protocol (*no less than 1-hour*).

6.4.2.2 Stress ¹³N-Ammonia PET

- Obtain baseline vital sign measurements and 12-lead ECG pre-injection of regadenoson or ¹³N-ammonia administrations. Continue to monitor ECG-rhythm, and HR, until stress PET MPI is completed;
- Administer regadenoson intravenous injection (0.4 mg/5 mL) over 10 sec, followed by 5-10 mL saline flush;
- Obtain vital signs (BP and HR) and 12-lead ECG as required per clinical protocol;
- 30 sec post regadenoson injection, administer an intravenous bolus injection of 10 mCi ± 20% (8–12 mCi) of ¹³N-ammonia followed by a 10 mL normal saline flush. If the same IV line is used for both the regadenoson and radiotracer injection, wait 10 to 20 seconds after the normal saline flush post regadenoson injection before injecting the radiotracer;
- Begin a 10-min list-mode data acquisition (if the anterior-posterior diameter of the chest is >50cm increase to 15-min) for a single bed position at the level of the heart immediately post-injection;
- Obtain vital signs (BP and HR) as described above prior to discharge.

7 SAFETY ASSESSMENTS

Safety will be evaluated by monitoring changes from screening or baseline assessments in vital signs, physical findings, electrocardiograms, clinical laboratory tests values, and the incidence of adverse events (AE). AEs will be reviewed for potential significance and clinical importance.

7.1 Clinical Laboratory Tests

The Department of Laboratories, Barnes-Jewish Hospital, is an accredited and Clinical Laboratory Improvement Act (CLIA) certified lab that will perform all laboratory blood tests for this study. A list of the current established reference ranges are available on the General Information page of the Barnes-Jewish Hospital (BJH) Lab website, <https://bjhlab.testcatalog.org/>.

All participants will have baseline blood and urine samples obtained for screening and for comparison with post-imaging complete blood count, comprehensive metabolic panel, and urinalysis. For abnormal changes from baseline, the Investigator or designee will determine if additional assessments for clinical significance or change in participant management if needed. Any adverse events/serious adverse events must also be documented in the case report forms (source documents) and appropriately reported.

Participants may request to receive a copy of their lab results or their rest/stress ¹³N-Ammonia PET MPI results to become part of their medical record at Barnes-Jewish Hospital.

7.2 Vital Sign Measurements

Vital sign (VS) measurements will be obtained at screening to determine eligibility, at baseline within 60-min, within 15-min pre-injection and within 5 min, 15-min, and hourly post-injection of

⁶⁸Ga-Galmydar, and end of imaging prior to discharge. VS measurements may be repeated as needed. Follow standard-of-care stress regadenoson and rest imaging clinical protocol for the N-ammonia imaging. VS measurements include heart rate (HR), systolic and diastolic blood pressure (BP), respiratory rate (RR), and body temperature. Temperature will be taken at baseline and prior to discharge on imaging days and as needed. Time points listed may only include BP and HR; see [Imaging PET Assessments](#) section for details. BP and HR must be obtained at least once prior to injection and once post-injection before discharge with the participant in the supine position. Care will be taken to obtain subsequent recordings with the participant in the same position (supine or upright).

The following variables are considered clinically significant if changes occur from baseline. A systolic BP of < 90 or > 160 mmHg or a diastolic BP of < 50 or > 100 mmHg or a 20 mmHg change from baseline in the SBP or DBP. A heart rate of < 50 BPM or > 100 or a 20 BPM change from baseline. A respiratory rate of < 12 or > 20 breaths/min and oral temperature of >100°F.

Participants who develop bradycardia (heart rate < 40 BPM, Mobitz 2:1 AV Block (Type 1 or Type 2) or QTc \geq 500ms) will be monitored until heart rate and conduction returns to baseline. Any abnormalities that meet the definition of an adverse event/ serious adverse event must be documented and appropriately reported.

7.3 12-lead electrocardiogram

A standard 12-lead electrocardiogram (ECG) will be obtained at screening for all participants. Baseline is within 60-min pre-injection, within 5-min post-injection, and prior to discharge, and repeated as needed. For the Rest/Stress group, ECGs will be obtained per standard-of-care rest/stress regadenoson imaging clinical protocol. A study cardiologist delegated by the PI will review and interpret the ECG, sign, and date.

The following variables are considered abnormal if changes occur from baseline. A PR interval of <120 or >200 msec, QRS interval <50 or >100 msec, RR interval <600 or >1000 msec, or QT interval \geq 500 msec. Participants who develop second or third degree AV block and/or QTc \geq 500 post-injection, will be monitored until the ECG returns to normal and will be excluded from additional study procedures. Any abnormalities that meet the definition of an adverse event/ serious adverse event must be documented and appropriately reported.

